11.1.3 Analysis Sets

The PPS will be used for the primary immunogenicity analysis and a supporting analysis will be performed using the FAS Immunogenicity. Duplicate tables of primary and secondary immunogenicity analyses may also be produced based on the FAS if there is $>1\%$ difference in the total number of subjects between the PPS and the FAS .

11.1.4 Statistical Methods

All statistical analyses for HI titers will be performed on the logarithmically transformed (base 10) values. Individual HI titers below the detection limit (<10) will be set to half of that limit (5).

Co-primary immunogenicity endpoints of GMT and SCR for each virus strain contained in the vaccine will be assessed for subjects ≥ 65 years overall. For A/H1N1 and A/H3N2 strains the two aTIV treatment groups will be pooled.

Primary analysis will be performed for subjects ≥ 65 years using the PPS. The difference in SCRs will be presented with exact 95% (CIs). Miettinen and Nurminen method may be used if convergence issues (Miettinen OS, Nurminen M., 1985). Each of the four strains will be analyzed separately.

To determine the GMT ratio (adjusted analysis) a general linear model (GLM) will be fitted on log transformed (base ten) post-vaccination HI titer as the outcome variable and terms for covariates: vaccine treatment, pre-vaccination HI titer, age stratum, sex, vaccination history, age-by-vaccine interaction and study site. Potential covariate interaction effects will also be examined in the fit of the GLM. From the model, an adjusted difference in least square means (on the log scale) will be produced with 95% confidence limits. The estimated difference and the confidence limits will be back-transformed to obtain an *adjusted GMT ratio* with 95% confidence limits. Each of the four strains will be analyzed separately. The adjusted GMT ratio will be the result for which the non-inferiority assessment of the HI GMT co-primary endpoint will be based on.

The statistical models might be reduced in case they fail to converge.

The complete set of covariates that may be used in the model to calculate the adjusted GMT ratio will include treatment group (3 treatments), age sub-group (3 categories, $\geq 65-74$, $\geq 75-84$, and ≥ 85 years), sex (male or female), influenza vaccination received prior year (Y or N), pre vaccination mean GMT titer (value) and investigator site (site identifier)

The GLM specification (for each strain) is:

- *Adjusted Analysis GMT Model:* Log10-transformed Post-vaccination HI Titer = Vaccine + Age Strata + Gender + Vaccination History [y/n] + Log10-transformed Pre-vaccination HI Titer + Site + Age Strata*Vaccine.

For any strain, the interaction term *Age Strata*Vaccine* will be removed from the fit of the model if it is assessed to be not significant at the 0.05 level.

The measure of the *unadjusted* GMT ratio (and CI's) based on post-vaccination GMTs only will also be presented.

In line with the FDA Guidance on seasonal inactivated influenza vaccines (*Guidance for Industry Clinical Data Needed to Support Licensure of Seasonal Inactivated Influenza Vaccines 2007*). aQIV will be considered to be noninferior to aTIV if, for each of the four strains, the following statistical criteria are met:

- The upper bound of the two-sided 95% Confidence Interval (CI) for the ratio of the GMTs does not exceed 1.5. The GMT ratio will be calculated by $\text{GMT}_{\text{aTIV}} / \text{GMT}_{\text{aQIV}}$
- The upper bound of the two-sided 95% CI for the difference between the SCRs does not exceed 10%. The difference in SCR will be calculated by $\pi_{\text{aTIV}} - \pi_{\text{aQIV}}$

To achieve the CBER criteria:

- The lower bound of the two-sided 95% confidence interval for the percentage of subjects achieving SC for HI antibody should meet or exceed 30%
- The lower bound of the two-sided 95% confidence interval for the percentage of subjects achieving an HI antibody titer $\geq 1:40$ should meet or exceed 60%

Binary data (ie, percentages of subjects with SC and with titer $\geq 1:40$) will be summarized for each group using unadjusted estimates and will be reported together with two-sided exact 95% CIs. No multiplicity adjustment to the CI levels will be implemented.

Handling of missing values for Immunogenicity Data:

For immunogenicity data, it may be reasonable to consider missing immunogenicity values as missing completely at random (MCAR), ie, not informative. Therefore, the key secondary analysis will comprise a complete case analysis only, without introducing any bias. Imputation methods will not be used.

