5. SAMPLE SIZE AND POWER CONSIDERATIONS

aQIV will be tested against aTIV comparators. The treatment randomization ratio is 2:1:1 (aQIV: aTIV-1: aTIV-2). This study is powered to achieve 80% power to demonstrate noninferiority over 8 co-primary endpoints, SCRs for 4 strains, GMT for 4 strains using a one-sided alpha of 0.025 for each comparison. No adjustment for multiple endpoints will be made.

For comparisons of SCR a noninferiority margin of 10% (aTIV – aQIV) will be employed. It is assumed that the SCRs for A/ H1N1, A/ H3N2 and B strains for TIV are 73%, 73% and 40% respectively. These estimates are based on the estimated SCR rates of historical data, namely study protocol V70_27. It has been assumed that there is no difference in terms of SCR between aQIV and aTIV for all strains. For comparison of the GMT ratio, a noninferiority of 1.5 (aTIV/aQIV) will be employed. It is assumed that there is no difference between aQIV and aTIV (i.e., a ratio of 1) and that the standard deviation (SD) of log (titer) is 1.2.

Under these assumptions, N FAS = 800 in the aQIV group and 400 in each aTIV group providing 800 and 800 subjects receiving aQIV and aTIV respectively for comparisons of A strains, and 800 and 400 subjects receiving aQIV and aTIV respectively for comparisons of B strains. This provides a total N FAS = 1600. These numbers provide 99.45% power to detect differences in SCR for each A strain and 91.29 % power for each B strain, providing overall 82.42% power for the 4 SCR tests.

For GMT ratio tests each A strain test will have 100% power and each B strain test will have 99.98% power, providing 99.96% power for the 4 GMT ratio tests and consequently 82.39% power for the 8 co-primary endpoints. Overall 1600 FAS subjects will be required. Allowing for a 10% drop-out N=1778 subjects will be recruited.

The immunogenicity was powered to meet the criteria pre-specified in the CBER guidance for acceptable immunogenicity: namely,

- the lower bound of the two-sided 95% confidence interval for the percent of subjects achieving SC should exceed 30%, and
- the lower bound of the two-sided 95% confidence interval for the percent of subject achieving HI antibody titer $\geq 1:40$ should exceed 60%

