11.3 Analysis of Exploratory Objectives

The exploratory objectives are:

1. Additional optional objectives include characterization of the immunogenicity of aQIV using other immunological assays (e.g., virus neutralization [MN] or anti-neuraminidase antibody assays may be performed)
2. To explore the association between immune response after administration of aQIV or the aTIV-1, containing the same virus strains as the US-licensed adjuvanted trivalent influenza vaccine, or the aTIV-2 containing the alternate B strain by baseline characteristics.

Exploratory immunogenicity objective 1

Exploratory objectives related to the MN-assay, immune response to heterologous influenza strains, or different antigens will be evaluated using similar methods for log normal, binomial data, and GMT and SCR as described in the statistical method for primary and secondary immunogenicity analysis.

Exploratory immunogenicity objective 2

- GMTs: Geometric mean of HI titers prevaccination (Day 1) and at Study Exit Visit
- Percentage of subjects with four-fold rise

Analyses of the exploratory immunogenicity endpoints will be performed with adjustment for covariates including prevaccination titer, vaccination history, age and gender to evaluate the contribution of these factors to variations in the immune response. The covariate adjustment will be performed with all of the specified covariates in the general linear model.

The full model specification for the GMT titers (for each strain) will be:

Log-transformed Post-Vaccination HI Titer = Vaccine + Age Strata + Gender + Vaccination History + Log-transformed Prevaccination HI Titer.

The full model specification for the SCR rates will be:

SCR = Vaccine + Age Strata + Gender + Vaccination History + Log-transformed Pre-vaccination HI titer

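### The co-primary SCR differences are compared without the baseline titer that the GMT model uses, a small missed gain in non-inferiority power

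*SAP*

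**What the plan says.** SAP 11.1.4, matched by Protocol 8.4.2.2.3, treats the two halves of co-primary objective 1 differently.

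- **GMT ratio.** Non-inferiority is decided on a general linear model with "terms for covariates: vaccine treatment, pre-vaccination HI titer, age stratum, sex, vaccination history, age-by-vaccine interaction and study site". An unadjusted ratio is also presented.
- **SCR difference.** "The difference in SCRs will be presented with exact 95% (CIs"), with Miettinen–Nurminen as a fallback for convergence problems. Binary endpoints "will be summarized for each group using unadjusted estimates and will be reported together with two-sided exact 95% CIs".
- **Covariate-adjusted SCR.** This appears only in SAP 11.3: "Analyses of the exploratory immunogenicity endpoints will be performed with adjustment for covariates including prevaccination titer, vaccination history, age and gender". It is a logistic regression reported as odds ratios, so it does not feed the 10-point margin decision.

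On power, SAP 5 states: "This study is powered to achieve 80% power to demonstrate noninferiority over 8 co-primary endpoints", "using a one-sided alpha of 0.025 for each comparison". SAP 2.4 counts the study as successful only if both co-primary objectives are met, so the CBER criteria must be met as well.

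**The concern.** Covariate adjustment is applied where power is already close to 100% and left out where it is lower. The stated power is 99.96% for the four GMT tests, 82.42% for the four SCR tests and 91.29% for each B-strain SCR test.

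Baseline titer is likely to predict seroconversion, because the definition changes at 1:10 and otherwise asks for a fourfold rise from the subject's own starting value. It is also complete. SAP 7.3 admits only subjects with Day 1 and Day 22 data, and the PPS is a subset of that set.

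Stratifying on baseline titer keeps the risk difference and the margin. It removes chance imbalance in baseline titer and narrows the interval somewhat. What is at stake is a modest amount of power on the two weakest non-inferiority tests, available only if specified before unblinding.

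**Working it through.** **Inputs from SAP 5 and Table 5-1**
- "It is assumed that the SCRs for A/ H1N1, A/ H3N2 and B strains for TIV are 73%, 73% and 40% respectively", with a true difference of 0.
- "For comparisons of SCR a noninferiority margin of 10" percentage points; one-sided alpha 0.025.
- 800 v 800 for A strains; 800 aQIV v 400 aTIV for B strains.
- SD of ln titer 1.2; B-strain titer ≥1:40 rate 64.6%.

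**Step 1: reproduce the plan's power**
- A score (Farrington–Manning) calculation gives 99.45% per A strain and 91.29% per B strain, as stated.
- The simpler Wald form for a B strain has SE = √[0.40 × 0.60 × (1/400 + 1/800)] = √0.0009 = 0.0300. Power = Φ(0.10/0.0300 − 1.960) = Φ(1.373) = 91.5%.
- Four SCR tests, treated as independent: 0.9945² × 0.9129² = 82.42%.
- With the GMT tests: 0.8242 × 0.9996 = 82.39%.

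**Step 2: locate the shortfall**
- The eight-endpoint shortfall is 100 − 82.39 = 17.61 points.
- The SCR tests alone give 100 − 82.42 = 17.58 points. The GMT tests alone give 0.04.

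**Step 3: how much baseline titer explains**

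The documents give no figure for this, so it is modelled. Pre- and post-vaccination titers are lognormal and read in twofold dilutions, calibrated to SCR 40%, post-titer ≥1:40 in 64.6% and post ln SD 1.2. Baseline ln SD (0.8–1.2) and pre/post correlation (0.3–0.7) are assumptions. With baseline ln SD 1.2:

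| Correlation | SCR at baseline <1:10 | 1:10 to <1:40 | ≥1:40 | Variance explained by 3 strata |
|---|---|---|---|---|
| 0.3 | 49% | 51% | 20% | 8.7% |
| 0.5 | 39% | 52% | 25% | 5.3% |
| 0.7 | 27% | 53% | 32% | 5.6% |

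With baseline ln SD 0.8, the three strata explain 2–4%. The overall range is about 2–9%. The relation is not monotone: the middle stratum seroconverts most often. At correlation 0.7 and baseline ln SD 1.0–1.2, a linear log-titer term explains only about 0.1%.

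**Step 4: convert to power**

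Multiply the Wald variance by (1 − R²), where R² is the share of SCR variance explained. The last column holds the A strains at 99.45%, so it is 0.9945² × (B power)² × 0.9996.

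| R² | B-strain SE | B-strain power | Eight endpoints |
|---|---|---|---|
| 0 | 0.0300 | 91.5% | 82.8% |
| 0.02 | 0.0297 | 92.0% | 83.7% |
| 0.05 | 0.0292 | 92.8% | 85.1% |
| 0.09 | 0.0286 | 93.8% | 86.9% |

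Simulation of stratified against crude differences over the same range of assumptions puts the gain at about 0.5–2.5 points per B strain. In one such run, one-sided error at a true 10-point deficit was 2.6–2.7% stratified against 2.5–2.7% crude, so there is no material loss of error control.

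The exact interval named in the plan was not simulated. A continuity-corrected proxy gives about 90.5% per B strain, so moving from exact to score may itself recover a little.

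**The case against.** **The plan is coherent as it stands.** Its power calculation assumes an unadjusted comparison, its analysis is unadjusted, and 82.39% exceeds the 80% target. This stands. A reader might infer that the SCR tests are underpowered or wrongly analysed, and the documents do not support that.

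**These tests do not set the power of the trial.** A reader might infer that they do, or that they are the co-primary tests most likely to fail. Neither holds. The CBER titer ≥1:40 criterion for the B strains has stated power 76.47%, and this change leaves it where it is. As an illustration only, treat all tests as independent and count both B strains: 0.7647² = 58.5%, and 58.5% × 82.39% = 48.2% for full success. Using the Step 4 range for the eight endpoints gives 0.585 × 83.7% = 49.0% to 0.585 × 86.9% = 50.8%.

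**There is a reason for the asymmetry.** The GMT ratio uses Day 22 titers only, so baseline can enter only through a model. SCR already compares each subject with his or her own baseline. The crude SCR also matches the CBER SCR criterion. This explains the choice and limits the gain, but categories of baseline titer still explain some variance at every setting tried.

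**The size of the gain is assumed.** This stands, and it is why a range is given. The documents do not show that high baselines always seroconvert least: at correlation 0.7 the ≥1:40 stratum does so more often (32%) than the <1:10 stratum (27%).

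**Conclusion.** The point holds as a missed efficiency confined to co-primary objective 1. The SCR comparisons carry 17.58 of the 17.61 points of shortfall in the stated non-inferiority power. They are the non-inferiority tests with room to gain, yet they are analysed without a complete baseline covariate that the GMT analysis already uses.

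The gain is about 0.5–2.5 points per B strain from about 91%. It rests on an assumed baseline ln SD of 0.8–1.2, an assumed pre/post correlation of 0.3–0.7, lognormal titers and the plan's own B-strain rates. It would be smaller still if baseline titer explains less than 2% of SCR variance. Nothing here shows that the planned analysis is invalid, and the change does little for the probability of overall success.

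**What to change.** Before unblinding, amend SAP 11.1.4 and Protocol 8.4.2.2.3 as follows.

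1. Make the deciding SCR difference a risk difference stratified by pre-vaccination titer for the strain concerned (<1:10, 1:10 to <1:40, ≥1:40). A stratified Miettinen–Nurminen interval with Mantel–Haenszel weights would serve. Keep the 10% margin and use the same method for all four strains.
2. Report the crude difference with its exact interval as supportive, mirroring the adjusted and unadjusted layout for GMT.
3. State in advance how strata are merged if one is empty in an arm.
4. Say whether the stratified method also applies to the secondary superiority comparison. SAP 11.2.1 takes its intervals from the primary method, so it would carry over by default.

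Do not standardise from the SAP 11.3 logistic model as written. Its continuous log-titer term can miss the non-monotone relation and so recover almost nothing.

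The cost is a few lines of wording and code, with no new data. There are two drawbacks. The deciding estimate will differ slightly from the crude percentages shown beside it, and an asymptotic stratified interval replaces the exact one.

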11.2 Analysis of Secondary Objectives

11.2.1 Analysis of Secondary Immunogenicity Objective(s)

Characterization of immunogenicity of aQIV, aTIV-1 and aTIV-2:

The measures of immunogenicity of aQIV, aTIV-1 and aTIV-2 will be assessed in terms of HI antibodies. Serum HI antibody titers against the 4 influenza vaccine strains will be used to calculate:

- GMT: Geometric mean of HI titers on Day 1 and Day 22

- GMR: The geometric mean of the fold increase of post-vaccination HI titer over the pre-vaccination HI titer (Day 22/Day 1)
- The percentage of subjects with a titer $\geq 1:40$ at Day 1 and Day 22
- SCR: the percentage of subjects with either a pre-vaccination HI titer $< 1:10$ and a post-vaccination HI titer $\geq 1:40$ or a pre-vaccination titer $\geq 1:10$ and a ≥ 4 -fold increase in post-vaccination titer on Day 22

Superiority of immunologic response for aQIV vs aTIV:

Superiority of aQIV over aTIV-1 and aTIV-2 for antibody response to the alternate B strain will be assessed using the adjusted GMT ratio (GMT_{aTIV}/GMT_{aQIV}) and difference in SCR ($SCR_{aTIV} - SCR_{aQIV}$) at Day 22. Point estimates and 95% confidence limits will be obtained as described for the primary endpoint. Superiority will be declared if the upper limit of the two-sided 95% CI for the difference in ($SCR_{aTIV} - SCR_{aQIV}$) is < 0 and the upper limit of the two-sided 95% CI for the GMT ratio (GMT_{aTIV}/GMT_{aQIV}) is < 1 for both B strains.

The same GLM as was used for the primary analysis will be used to determine the adjusted GMT ratio for assessing superiority.

11.2.2 Statistical Hypotheses

No statistical testing will be performed for the first secondary immunogenicity objectives.

Superiority of B-strain response (GMTs and proportions of subjects with SC):

For superiority of aQIV B strain response, the hypotheses are that immunologically aQIV is superior compared to aTIV-1 and aTIV-2 for the B strain that is not included in each TIV vaccine separately. In mathematical form, these are:

$$H_{0k}^{(GMT)}: GMTr_k \geq 1 \text{ vs } H_{1k}^{(GMT)}: GMTr_k < 1 \text{ for } k=1,2$$

and

$$H_{0k}^{(SCR)}: D_k \geq 0 \text{ vs } H_{1k}^{(SCR)}: D_k < 0 \text{ for } k=1,2$$

where $GMTr_k$ is the adjusted ratio of geometric mean titer GMT_{aTIV-k}/GMT_{aQIV} of mismatched B strain for $k=1, 2$, and D_k is the differences $\pi_{aTIV-k} - \pi_{aQIV}$ of mismatched B strain Day 22 SCR differences for $k=1,2$.

11.2.3 Analysis Sets

The secondary objective superiority testing will be performed using the PPS.

11.2.4 Statistical Methods

All statistical analyses for HI titers will be performed on the logarithmically transformed (base 10) values. Individual HI titers below detection limit (<10) will be set to half of that limit (5).

Unadjusted GMTs, GMRs and pertaining two-sided 95% CIs will be calculated assuming log-normal distribution of the titers and will be completed by providing minimum, maximum and median titers for each vaccine group.

Binary data (ie, percentages of subjects with SC and with titer $\geq 1:40$) will be summarized for each group using crude estimates and will be reported together with 2-sided exact 95% CIs. No multiplicity adjustment to the CI levels will be implemented.

For immunogenicity data, it may be reasonable to consider missing immunogenicity values as missing completely at random (MCAR), i.e., not informative. Therefore, the key secondary analysis will comprise a complete case analysis only, without introducing any bias. Imputation methods will not be used.

The following figures will be also produced:

- GMT Reverse Cumulative Distribution Curve – Overall by Strain
- GMT Reverse Cumulative Distribution Curve – by Age Cohort
- GMT Reverse Cumulative Distribution Curve – by Study Treatment

11.2.5 Analysis of Secondary Safety Objective(s)

The analysis of safety assessments in this study will include summaries of the following categories of safety data collected for each subject:

- Vaccine exposure.
- Solicited local and systemic AEs.
- Unsolicited AEs.
- SAEs, AE leading to withdrawal, NOCD, AESI

11.2.5.1 Analysis of Extent of Exposure

The numbers and percentages of subjects with vaccinations will be summarized overall and by vaccine group. Data will be tabulated for the Exposed Set.

11.2.5.2 Solicited Adverse Events

The safety completeness analysis on solicited AEs aims to identify subjects who completed diary cards, irrespective of severity. The analysis will show the number of subjects with valid data by solicited AE and time point. Valid data in the context of the safety completeness analysis are all data entered in the diary card (including implausible values) except “Not done/unknown”.

Four summaries will be produced:

1. The frequencies of subjects who provide diary cards by vaccine group.

2. For each solicited AE, the frequencies of subjects with valid data will be presented by vaccine group and timepoint: 30 min, 6h –Day 3, Day 4-7, 6h - Day 7, Day 1 – 7 (with/without 30 mins).
3. For each type of solicited AE (local, systemic) and indicators of solicited AEs, such as analgesic use, the frequencies of subjects with valid data by vaccine group, aggregated over time points: 30 min, 6h –Day 3, Day 4-7, 6h - Day 7, Day 1 – 7 (with/without 30 mins).
4. For each solicited AE, the frequencies of subjects with valid data by vaccine group, aggregated over time points: 30 min, 6h –Day 3, Day 4-7, 6h - Day 7, Day 1 – 7 (with/without 30 mins).
5. For the corresponding percentages, the denominator will be the respective numbers of exposed subjects, i.e., subjects who received a vaccination and were still in-study for that time point or time interval, irrespective of whether a diary card was present or not.

All analyses will be based on the ‘as treated’ Solicited Safety Set.

11.2.5.3 Solicited Local and Systemic AEs

For details please refer to section 7.1.1 of the protocol.

Only solicited local and systemic AEs reported in the diary card will be analyzed. Implausible measurements will not be taken into consideration in the analysis (see section 6.3).

Solicited AEs will be reported at 30 minutes, at 6 hours on Day 1 and then daily until Day 7 using structured diaries. The analyses of solicited AEs will be done separately for 30 minutes and based on three intervals: 6h - Day 3, Day 4 - 7 and 6h - Day 7, each without 30 minutes’ data. In addition, solicited AEs ongoing after Day 7 will be presented as unsolicited AE.

For erythema, induration, and ecchymosis recorded originally as diameters (mm), the following categorization will be used to summarize the data:

Type I: none (0 mm), any (1-24 mm, 25-50 mm, 51-100 mm, >100 mm)

Type II: Grade 0 (< 25 mm), any (25-50 mm, 51-100 mm, >100 mm)

Body temperature will be broken down by route of measurement according to the recommendations of the Brighton collaboration as well as CBER and will be summarized according to the 3 schemes described below:

- Brighton:
 - <38.0,
 - 38.0 - 38.4
 - 38.5 - 38.9
 - 39.0 - 39.4
 - 39.5 - 39.9
 - 40.0 – 40.4
 - 40.5 – 40.9

- $\geq 41.0^{\circ}\text{C}$
- CBER:
 - 38.0–38.4
 - 38.5–38.9
 - 39.0–40.0
 - $>40^{\circ}\text{C}$
- $<38.0, \geq 38.0^{\circ}\text{C}$

Fever, defined as a body temperature of $\geq 38^{\circ}\text{C}$ irrespective of route of measurement, will be integrated to the summaries as a systemic AE.

The analyses will encompass summaries of the data on five levels:

1. Daily reports of subjects with solicited AEs.
2. Time of first onset of solicited AEs 30 min measurement (after 30 minutes).
3. Solicited AEs, maximum event severity by event and interval 6h - Day 3, Day 4 -7, and 6h - Day 7, each without 30 min.
4. Duration of solicited AEs, including ongoing AE after Day 7.
5. Solicited AEs and indicators of solicited AEs, occurrence of at least one event by category (local, systemic) and interval 6h-Day 3, Day 4-7 and 6h-Day 7, each without 30 min.

For each of the time points or time intervals presented in the summaries, only subjects with at least one plausible observation (i.e., any non-missing values but excluding “Not done/unknown” and implausible values) for the solicited AEs in the interval of interest will be considered. Subjects without plausible data (i.e. missing values or reported as “Not done/unknown” and implausible values) will be removed from the denominator to prevent a downward bias (towards zero).

Level 1: Daily reports of solicited AE

For each of the time points only subjects with at least one plausible observation (i.e., any non-missing values but excluding “Not done/unknown” and implausible values) for the solicited AE in the interval of interest will be considered. Subjects without plausible data (i.e. missing values or reported as “Not done/unknown” and implausible values) will be removed from the denominator in order to prevent a downward bias (towards zero). Data collected will be summarized (frequencies and percentages of subjects) by vaccine group, solicited AE, vaccination number and time point.

Level 2: Time of first onset of solicited AEs

The **time of first onset** is defined, for each subject, for each solicited AE, as the time point at which the respective solicited AE first occurred. For erythema, induration, and ecchymosis the

following threshold will be used: ≥ 1 mm. The summary will provide the frequencies and percentages of subjects with first onset of each solicited AEs by vaccine group and by each time point.

The following example is used to illustrate how the onset data is selected:

Suppose four subjects, who receive vaccination A, have the following post-vaccination data for solicited AE XY

Table 11-1: Example for Time to First Onset of Solicited Adverse Events

Vaccination	Subject Number	6 Hours	Day 2	Day 3	Day 4	...	Day 7
1	001	None	Severe	Moderate	None	...	None
	002	Mild	None	None	Moderate	...	Missing
	003	Moderate	Mild	None	Severe	...	Mild
	004	Mild	Mild	None	None	...	Not done

Level 3: Solicited AEs, maximum event severity by event and interval

The **maximum event severity** will be defined if there is at least one plausible non-missing observation (excluding “Not done/unknown” and implausible values) within this time interval. Each subject’s data will be aggregated across the time points of the interval and summarized according to the maximal severity observed for each AE, followed by a summary across subjects for each vaccine. Subjects without any solicited AEs in the interval, i.e., missing values at each of the requested time points, will be removed from the denominator.

Level 4: Number of days with solicited AEs

The number of days with the AE is defined irrespective of severity. This means at least ‘mild’ solicited AE that are assessed qualitatively and ≥ 1 mm for erythema and induration and ecchymosis. If a solicited AE continues beyond Day 7 the date of resolution is recorded and the entirety of the duration is included in the calculation. The following example is used to illustrate how the duration is calculated:

Suppose six (6) subjects, who received a vaccination have the post-vaccination solicited AE data shown in the table below. In addition, there are unsolicited AE reports indicating that the AE in subject 003 and 006 continued until Day 12 and Day 8, respectively. For subject 003 the number of days is calculated as 6+5 and for subject 006 as 3+1. Missing values (‘Missing’) are not taken into consideration

Table 11-2: Example for Number of Days with Solicited Adverse Events

Subject Number	6 Hours	Day 2	Day 3	Day 4	Day 5	Day 6	Day 7	No. of days
001	None	Severe	Moderate	None	None	None	None	2

Subject Number	6 Hours	Day 2	Day 3	Day 4	Day 5	Day 6	Day 7	No. of days
002	Mild	None	None	Moderate	Moderate	Moderate	Missing	4
003	Moderate	Mild	None	Severe	Severe	Severe	Mild ^a	11
004	None	None	None	None	None	None	Not done	0
005	None	Mild	Mild	Missing	Missing	Missing	Missing	2
006	Severe	None	Mild	None	None	None	Severe ^b	4

^a continued until Day 12; ^b continued until Day 8

The frequency distribution of the number of days will be provided in a summary table by vaccine and by AE.

Level 5: Solicited AEs, occurrence of at least one event by category (local, systemic) and interval.

The **occurrence of at least one solicited AE** is defined as “any” for a subject if he/she reports greater than “none”, ≥ 1 mm for erythema, ecchymosis and induration) for the respective event and “none” otherwise. The occurrence of at least one solicited AE (i.e., none versus any) will be summarized by category (i.e., local, systemic, any), by vaccine group, by vaccination (after each vaccination and after any vaccination) and by time interval.

Medications to treat or prevent pain or fever will be summarized by frequencies and percentages of subjects reporting use of the medications by interval 30 min, 6h - Day 3, Day 4 - 7, and 6h - Day 7.

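### The Level 4 table of days with a solicited AE reports minimum counts as exact when diary days are missing

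*SAP*

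**What the plan says.** SAP 11.2.5.3 lists five levels of solicited-AE summary. The list presents Level 4 as the duration of solicited AEs, including those ongoing after Day 7. The rules are:

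- Any recorded day at mild or above, or at 1 mm or more, counts: "The number of days with the AE is defined irrespective of severity".
- Missing values "are not taken into consideration".
- Events that outlast the diary are extended: "If a solicited AE continues beyond Day 7 the date of resolution is recorded and the entirety of the duration is included in the calculation".
- Output from this level: "The frequency distribution of the number of days will be provided in a summary table by vaccine and by AE".

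Table 11-2 applies these rules to six invented subjects. Three rows matter most (columns run from 6 hours and Day 2 to Day 7, then the number of days):

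- "001 None Severe Moderate None None None None 2"
- "002 Mild None None Moderate Moderate Moderate Missing 4"
- "005 None Mild Mild Missing Missing Missing Missing 2"

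Earlier in the same section, subjects with no plausible data for a time point or interval "will be removed from the denominator to prevent a downward bias (towards zero"). One plausible observation is enough to keep a subject in.

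**The concern.** Subjects 001 and 005 both get 2 days. Subject 001 has a complete diary in which the reaction is gone by Day 4. Subject 005 was still reacting at the last entry, and four of the seven time points are blank. The first value is an observation and the second is a floor, but the table gives the reader no way to tell them apart. Events known to run past Day 7 (subjects 003 and 006) are followed to resolution and counted in full, and they go into the same distribution.

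The table is produced by vaccine and by AE and will be read as a description of how long reactions last. If incomplete diaries are common, it will understate duration without any sign on its face. Protocol 3.4.2 makes blanks permanent: nothing may be added once the card is delivered, and blank fields are entered as missing. SAP 8.2.1 rules out imputation.

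**Working it through.** **1. Reproducing Table 11-2.** Count = recorded time points with the AE + known days after Day 7, with every Missing or Not done entry contributing 0. The upper bound counts each unrecorded diary day as an event day, within the window to Day 7.

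| Subject | Recorded event days | After Day 7 | Count | SAP value | Unrecorded days | Possible range |
|---|---|---|---|---|---|---|
| 001 | 2 | 0 | 2 | 2 | 0 | 2 |
| 002 | 4 | 0 | 4 | 4 | 1 | 4 to 5 |
| 003 | 6 | 5 | 11 | 11 | 0 | 11 |
| 004 | 0 | 0 | 0 | 0 | 1 | 0 to 1 |
| 005 | 2 | 0 | 2 | 2 | 4 | 2 to 6 |
| 006 | 3 | 1 | 4 | 4 | 0 | 4 |

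All six SAP values reproduce when each unrecorded day counts 0. The SAP never calls such a day event-free, but the arithmetic is the same. Subject 004's Not done entry is handled this way too, although the sentence names only missing values. The mean over the six is 23/6 = 3.83 as scored and at most 29/6 = 4.83. These rows are a teaching example, so they show the rule and not how often it bites.

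**2. Direction.** An unrecorded day can be worth 0 or 1 and is always scored 0. The count can therefore be too low but never too high.

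**3. Size under stated assumptions.** The documents give neither reaction durations nor diary-completion rates, so these inputs are assumed:

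- the reaction starts on diary day 1 and persists each day with probability q;
- the diary stops after any given day with probability h, unrelated to the reaction;
- counting is capped at 7 days, with no follow-up beyond.

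With r = q(1 − h), the share with at least k counted days is r^(k−1). The mean is therefore (1 − r^7)/(1 − r), and the share with 4 or more days is r³. Setting h = 0 gives the true values.

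| q | Mean, true | Mean, h = 2% | Mean, h = 10% | ≥4 days, true | ≥4 days, h = 2% | ≥4 days, h = 10% |
|---|---|---|---|---|---|---|
| 0.3 | 1.43 | 1.42 | 1.37 | 2.7% | 2.5% | 2.0% |
| 0.5 | 1.98 | 1.95 | 1.81 | 12.5% | 11.8% | 9.1% |
| 0.7 | 3.06 | 2.96 | 2.60 | 34.3% | 32.3% | 25.0% |

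For q = 0.7 and h = 10%, for example, r = 0.63, the mean is (1 − 0.0394)/0.37 = 2.60, and r³ = 0.250.

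**4. A second model.** Onset is on day 1 (70%) or day 2 (30%), with geometric duration of mean 2.5 days cut at Day 7. The simulated true mean is 2.42 days. If 10% of subjects stop the diary between Days 2 and 4, the scored mean is 2.31, a loss of 0.11 day. The share with 4 or more days falls from 21.6% to 19.5%.

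**The case against.** Four points on the other side have force.

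- **Level 4 is not an exception to a safeguard.** A reader might infer that the SAP protects its other summaries from this bias and forgets Level 4. The text does not support that. The denominator rule removes only subjects with no plausible data. Levels 3 and 5 keep partly completed diaries just as Level 4 does, and only a summary at a single time point (Level 1) fully drops a missing day.
- **Duration is not a named endpoint.** Protocol 8.1.3 and SAP 2.2.4 define the safety endpoints by frequency and severity. No hypothesis, success criterion or sample size depends on this table.
- **A stopped diary is not always scored as a stopped reaction.** Protocol 7.1.1 sends solicited AEs that continue beyond Day 7 to the AE CRF, the Day 15 call and Day 22 interview can pick them up, and Level 4 adds the later days. This stands in part. It does nothing for events that ended within the unrecorded days, and the SAP does not say whether a gap before Day 7 is then filled.
- **Missingness is reported.** SAP 8.2.1 and 11.2.5.2 give missing-assessment percentages and valid-data counts, the latter by vaccine group, AE and time point. Uneven diary completion would show there, but those totals do not reveal which durations were cut short.

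None of this makes the values for subjects 002 and 005 exact.

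**Conclusion.** The point holds for a descriptive safety table. Level 4 presents lower bounds as exact durations, and its frequency distribution can err only toward shorter reactions. In the first model the mean count drops by 0.01 day (q = 0.3, h = 2%) to 0.46 day (q = 0.7, h = 10%). All of these figures rest on assumed inputs, and stopping the diary because of the reaction could make the effect larger.

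It is tempting to go further and say that longer reactions to aQIV could be hidden. The documents do not support that. A difference between arms would need differing diary completion or differing durations. No figure is given for either, and the vaccines are blinded and look alike (Protocol 3.3). The co-primary and secondary immunogenicity conclusions are untouched.

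**What to change.** Amend SAP 11.2.5.3, Level 4, before unblinding:

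- Keep all subjects in the table and in its denominator.
- Where a diary has any Missing or Not done day that could add to the count, report that count in a separate row, 'at least n days (incomplete diary)', by vaccine and AE.
- Extend the missing-value sentence to cover Not done.
- In Table 11-2, mark subjects 002, 004 and 005 as ≥4, ≥0 and ≥2.

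Do not make a complete-diary distribution the main result; use it at most as a sensitivity table. Keeping only diaries complete to Day 7 or to resolution drops people who were still reacting, and so favours short events. In the second model with 10% stopping, it gives a mean of 2.36 to 2.38, depending on whether the stopping day itself is recorded, against a true 2.42. Resolution is also hard to define when events recur after a clear day, as for subjects 002, 003 and 006.

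The cost is a change of wording and a few extra rows per table. No new data and no change in trial conduct are needed.
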